4.1 Inclusion Criteria

4.1.1 MDS with WHO classification of RA, RARS, RCMD-RS, and RCMD and RAEB-1

4.1.2 Anemia requiring transfusion support with at least one unit of packed red blood cells per month for greater than or equal to 2 months

OR

Anemia (hemoglobin <9 or a reticulocyte count <60,000)

OR

thrombocytopenia (platelet count less than 50000/ μ L)

OR

neutropenia (absolute neutrophil count less than 500/ μ L).

- 4.1.3 Off all other treatments for MDS (except filgrastim [G-CSF]), erythropoietin, and transfusion support and related medications) for at least four weeks. Filgrastim (G-CSF) can be used before, during and after the protocol treatment for patients with documented neutropenia (<500/Ul) as long as they meet the criteria for anemia and/or thrombocytopenia as stated above.
- 4.1.4 Ages 18-72 (inclusive)

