8.0 BIOSTATISTICAL CONSIDERATIONS

8.1 Primary Endpoint

The primary endpoint is hematologic response measured at 3 months after first dose alemtuzumab (Campath®) sustained on at least two serial measurements at least one week apart at landmark time points (3, 6 and 12 months) will be defined using standard hematologic and cytogenetic response criteria for MDS (See Appendix B for detailed description)⁷⁷.

Complete response: Normalization of all affected cell lines (Hemoglobin, Reticulocyte count, Platelets, ANC)

Partial response: At least one minor response

1. Hemoglobin Response

Major response: For subjects with pretreatment hemoglobin less than 11 g/dL, greater than 2 g/dL increase in hemoglobin; for RBC transfusion-dependent subjects, transfusion independence or an absolute reticulocyte count to $\geq 60,000/\mu\text{L}$ of blood in transfusion-dependent patients.

Minor response: For subjects with pretreatment hemoglobin less than 11 g/dL, 1 to 2 g/dL increase in hemoglobin; for RBC transfusion-dependent patients, 50% decrease in transfusion requirements.

2. Platelet response

Major response: For subjects with a pretreatment platelet count less than $100,000/\text{mm}^3$, an absolute increase of $30,000/\text{mm}^3$ or more; for platelet transfusion-dependent subjects, stabilization of platelet counts and platelet transfusion independence.

Minor response: For subjects with a pretreatment platelet count less than 100,000/mm³, a 50% or more increase in platelet count with a net increase greater than 10,000/mm³ but less than 30,000/mm³.

3. ANC response

Major response: For absolute neutrophil count (ANC) less than 1500/mm³ before therapy, at least a 100% increase, or an absolute increase of more than 500/mm³ whichever is greater.

Minor response: For ANC less than 1500/mm³ before therapy, ANC increase of at least 100%, but absolute increase less than 500/mm³.

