8.2 Secondary Endpoints

8.2.1 Transfusion-independence for red blood cells and/or platelets: ability to maintain a hemoglobin >8gm/dl and a platelet count > 20 000/ μ L without the need for transfusions for a period of 6 weeks regardless of subsequent events.

8.2.2 Overall survival which is defined as the time elapsed between time of treatment and death and will be compared between responders and non-responders. Any such comparison may be biased and needs to be interpreted cautiously.

8.2.3 Life threatening toxicity. Subjects who do not complete the treatment course because of toxicity or voluntary withdrawal will be included in analyses.

8.2.4 Overall survival and transformation-free survival, which is defined as the time elapsed (reported at 3 month intervals for the first four years, then yearly thereafter) between time of treatment, and bone marrow morphologic evidence for progression (as determined by FAB criteria), development of acute leukemia, or death will be compared between responders and non-responders. Any such comparison may be biased and needs to be interpreted cautiously.

8.2.5 Response duration will be determined as the interval between time of onset of response as outlined above, and the time of relapse or loss of response characteristic (reported at 3 month intervals for the first four years, then yearly thereafter).

8.2.6 Affects of the addition of cyclosporine. Subjects who relapse after responding to Campath will be given CsA to determine if CsA will be beneficial under these circumstances. For this protocol, CsA is investigational, subjects will be followed, data will be collected and analyzed as secondary endpoints. The number of subjects who will receive CsA cannot be predicted since it will depend on the initial response to Campath which is unknown.

Response proportion, response duration, overall survival, and transformation free survival will be determined and compared within the FAB sub-groups and International Prognostic Scoring System categories of MDS and with the results of previous studies at the NIH using h-ATG alone or CsA alone to treat the cytopenia of MDS.

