8.3 Sample Size

Because the efficacy of this treatment is almost completely unknown, we would like to reject the treatment as quickly as possible with a small number of subjects if the treatment is not effective.

A response probability of 30% or less would warrant terminating the treatment on this subject population, and we hypothesize that the actual response probability using this treatment would reach 50% or more.

Let p be the probability of complete or partial response at 3 months. Our sample size is determined by testing the null hypothesis $H_0: p \leq 30\%$ versus the alternative $H_1: p \geq 50\%$ at 0.05 significance level and 0.80 of the power. We determine the sample size using the Two-Stage Minimax Design outlined in Table 1 of Simon (1989)⁷⁵ This design is selected because it requires a smaller total number of subjects ($n=39$) than the Simon's Two-Stage Optimal Design ($n=46$). At the first stage, 19 subjects will be accrued and the null hypothesis will be accepted (i.e., the treatment will be terminated) if 6 or less subjects respond to the treatment at 3 months. If 7 or more subjects respond to the treatment at 3 months in the first stage, then an additional 20 subjects will be accrued, bringing the total number of subjects to $n=39$. The null hypothesis of $p \leq 30\%$ will be accepted if the total number of complete and partial responders at 3 months is 16 or less.

An additional 39 subjects will be enrolled to allow for statistically valid subgroup comparisons of secondary endpoints such as response to cyclosporine in subjects who relapse within six months of treatment.

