If. Disease transformation: Transformation to AML (30% or more blasts).

Ig. Survival and progression-free survival

II. Cytogenetic response

IIa Major: No detectable cytogenetic abnormality, if preexisting abnormality was present.

IIb Minor: 50% or more reduction in abnormal metaphases.

Requires 20 analyzable metaphases using conventional cytogenetic techniques. Fluorescent in situ hybridization may be used as a supplement to follow a specifically defined cytogenetic abnormality.

III. Hematologic Improvement (HI)

Improvements must last at least 2 months in the absence of ongoing cytotoxic therapy.† Hematologic improvement should be described by the number of individual, positively affected cell lines (eg, HI-E; HI-E 1 HI-N; HI-E 1 HI-P 1 HI-N).

IIIa. Erythroid response (HI-E)

- *Major response:* For patients with pretreatment hemoglobin less than 11 g/dL, greater than 2 g/dL increase in hemoglobin; for RBC transfusion-dependent patients transfusion independence.
- *Minor response:* For patients with pretreatment hemoglobin less than 11 g/dL, 1 to 2 g/dL increase in hemoglobin; for RBC transfusion-dependent patients, 50% decrease in transfusion requirements.

IIIb. Platelet response (HI-P)

- *Major response:* For patients with a pretreatment platelet count less than 100 000/mm³, an absolute increase of 30 000/mm³ or more; for platelet transfusion-dependent patients, stabilization of platelet counts and platelet transfusion independence.
- *Minor response:* For patients with a pretreatment platelet count less than 100 000/mm³, a 50% or more increase in platelet count with a net increase greater than 10,000/mm³ but less than 30,000/mm³.

IIIc. Neutrophil response (HI-N)

- *Major response:* For absolute neutrophil count (ANC) less than 1500/mm³ before therapy, at least a 100% increase, or an absolute increase of more than 500/mm³, whichever is greater.
- *Minor response:* For ANC less than 1500/mm³ before therapy, ANC increase of at least 100%, but absolute increase less than 500/mm³.

IIId. Progression/relapse after HI:

One or more of the following: a 50% or greater decrement from maximum response levels in granulocytes or platelets, a reduction in hemoglobin concentration by at least 2 g/dL, or transfusion dependence.§

For a designated response (CR, PR, HI), all relevant response criteria must be noted on at least 2 successive determinations at least 1 week apart after an appropriate period following therapy (eg, 1 month or longer).

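### Section 8.1 lets a still-transfused subject count as a major responder on reticulocytes of 60,000/µL or more alone, a route absent from the Appendix B criteria it cites, and no response rate without that route is planned

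*Combined protocol and SAP*

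**What the plan says.** Section 8.1 states that response follows standard MDS criteria and refers to Appendix B for the detail. For a major hemoglobin response it then asks, "for RBC transfusion-dependent subjects, transfusion independence or an absolute reticulocyte count to" 60,000/µL or more. Appendix B IIIa (HI-E), major response, reads "for RBC transfusion-dependent patients transfusion independence" and stops there. Its minor response for the same patients is a halving of transfusion need. Neither level mentions reticulocytes.

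The two texts also differ on duration. Section 8.1 wants the response "sustained on at least two serial measurements at least one week apart at landmark time points" (3, 6 and 12 months). Appendix B III says "Improvements must last at least 2 months in the absence of ongoing cytotoxic therapy".

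Entry under section 4.1.2 is by any one of four alternatives. One is "Anemia requiring transfusion support with at least one unit of packed red blood cells per month" for at least 2 months. A separate one is "Anemia (hemoglobin <9 or a reticulocyte count <60,000"). A subject entering by the first need not meet the second.

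In section 8.1 one minor response is enough for a partial response. Section 8.3 lets p "be the probability of complete or partial response at 3 months", continues after stage 1 on 7 or more responders of 19, and rejects the null on 17 or more of 39.

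**The concern.** A subject who is transfused as often after treatment as before, with no hemoglobin gain, can count as a major responder if the reticulocyte count is 60,000/µL or more. Because no baseline level is stated, this could on the literal wording include someone already at that count on entry, in whom nothing has changed. Each such subject adds one to the tally for the 7/19 and 17/39 decisions.

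The planned analyses in section 8.4 give only the proportion with complete or partial response. A reader of the results could not tell whether the go/no-go decision rested on subjects with neither transfusion nor hemoglobin benefit.

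There is also a possible mismatch in the comparison that section 8.2 plans "with the results of previous studies at the NIH using h-ATG alone or CsA alone to treat the cytopenia of MDS". Section 2.4.1 reports those studies as transfusion independence (21 of 61 and 3 of 18). If those are the comparators, a still-transfused reticulocyte-only responder would count here but not there.

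**Working it through.** **1. The texts side by side, for a transfusion-dependent subject**

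| Route to erythroid response | Section 8.1 | Appendix B HI-E |
|---|---|---|
| Transfusion independence | major | major |
| 50% fall in transfusions | minor | minor |
| Reticulocytes 60,000/µL or more | major | not listed |
| Baseline reticulocyte condition | none stated | not applicable |

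Duration does not close the gap. If the 2-month rule in Appendix B governs, fewer subjects would qualify, but that rule does not ask about transfusions for this route either.

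**2. The plan's own design**

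Inputs from section 8.3: null 0.30, alternative 0.50, stage 1 of 19 (stop at 6 or fewer), total 39 (accept the null at 16 or fewer).

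P(success | p) = Σ over x = 7 to 19 of P(X₁ = x) · P(X₂ ≥ 17 − x), with X₁ ~ Bin(19, p) and X₂ ~ Bin(20, p).

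- p = 0.30: 0.0455
- p = 0.50: 0.8036

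An exhaustive search for the minimax design returns the same boundaries (6/19, 16/39). The stated design is correct for response as scored.

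**3. How far the route could move the decision, relative to a different endpoint**

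Suppose response under HI-E plus the platelet and ANC routes is exactly 30%, and a share d of the remaining 70% qualifies by reticulocytes only. Then the scored rate is p = 0.30 + 0.70d, and the expected number of such subjects in 39 is 39 × 0.70 × d. The documents give no value for d, so every row is an assumption.

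| d | p scored | Expected in 39 | P(success) |
|---|---|---|---|
| 0 | 0.300 | 0 | 0.0455 |
| 1% | 0.307 | 0.27 | 0.0556 |
| 2% | 0.314 | 0.55 | 0.0673 |
| 5% | 0.335 | 1.4 | 0.1128 |
| 10% | 0.370 | 2.7 | 0.2260 |

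For scale, d = 5% would arise if half of the remaining subjects were transfusion-dependent and 1 in 10 of those qualified (0.5 × 0.1 = 0.05). Both shares are assumed.

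**The case against.** **The route is a choice, not a slip.** The synopsis names changes in blood counts, reticulocytes included, as primary endpoints. Section 8.1 lists reticulocytes among the lines to normalize for a complete response, and 60,000 mirrors the entry threshold. This stands, and it is why the written primary should stay.

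**A rise was meant.** The word "to" before the threshold, and the synopsis's reference to changes, both point that way. This largely stands. The baseline gap is one of wording, but section 8.1 does not close it and section 4.1.2 leaves it open.

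**Transfusion benefit is already reported.** Section 8.2.1 plans transfusion independence for 6 weeks, and the synopsis plans the decrease in transfusions. Neither uses reticulocytes, so a reader who inferred that no result without the route is planned would be wrong. But 8.2.1 uses its own definition (hemoglobin above 8 g/dL, platelets above 20,000/µL) and gives no credit for a 50% reduction. Neither result shows how many counted responders depend on reticulocytes alone.

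**Few subjects can qualify.** The route is open only to transfusion-dependent subjects. After treatment, reticulocytes are scheduled only at months 1, 3 and 6 and then yearly (sections 6.3 to 6.5), so a repeat close to month 3 may not exist. This stands and limits the size of the problem.

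**The comparator is inferred.** Section 8.2 does not say that the figures in 2.4.1 will be used, and section 2.5.7 reports response rates for the same drugs. Minor, platelet and ANC responses, and the exclusion of low-probability patients (4.2.12), also separate the studies. The mismatch is therefore only possible, and the route is one part of it.

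**Conclusion.** The point holds as a reporting gap. As written, section 8.1 admits responders with no transfusion or hemoglobin benefit, by a route that its cited criteria lack, and neither the response rate nor the 7/19 and 17/39 decisions are to be shown without it.

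A reader might infer from the table that the type I error is inflated. The documents do not support that. Section 8.3 tests response as section 8.1 scores it, and for that quantity the error rates are 0.0455 and 0.804. The values from 0.0556 to 0.2260 describe a different endpoint under assumed d; at d of 1% to 2%, fewer than one such subject is expected in 39. Nor do the documents show that counts raised by alemtuzumab-related hemolysis will be scored as response. Section 10.3.1 lists autoimmune hemolytic anemia as a risk, but nothing indicates how often it would produce a reticulocyte-only responder.

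The number affected is unknown and probably small. This is an improvement to consider, not an error in the design.

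**What to change.** Keep the section 8.1 rule as the written primary analysis and add two items.

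1. The number of responders who qualify only by the reticulocyte route, among the first 19, the 39 and all treated. For each, give the baseline reticulocyte count, identifying anyone already at 60,000/µL or more (who shows no change), and state whether a confirming count exists.
2. The primary result a second time, on the same denominators, with transfusion-dependent subjects scored by Appendix B HI-E (transfusion independence or a 50% reduction) plus the platelet and ANC routes, labelled as a sensitivity analysis.

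Optionally, note any reticulocyte-only responder with a positive DAT and raised LD or indirect bilirubin. This would be descriptive and remove no one.

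The work is feasible although section 10.4 places the study in data analysis only. Reticulocytes are scheduled at baseline and month 3, and transfusion data are already needed for the other routes. The cost is one extra analysis and a second rate that may be slightly lower. HI-E scoring also gives no credit for early marrow recovery that has not yet cut transfusions, which is a reason to keep it as a sensitivity analysis. If item 1 returns zero, one line settles the matter.

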One such novel therapy, alemtuzumab (Campath®) is a humanized IgG1 monoclonal antibody directed against the CD52 protein, which is highly expressed on all lymphoid cells and monocytes. Alemtuzumab (Campath®) produces profound and persistent lymphopenia, affecting predominantly the CD4+ T cell subset. This property has made it attractive in the treatment of a wide range of diseases including rheumatoid arthritis, multiple sclerosis, ocular inflammatory disease, lymphoid malignancies, organ allograft rejection, and in conditioning regimens in stem cell transplantation to prevent graft failure and graft-versus-host disease.

We therefore propose a non-randomized, off label, pilot, Phase I/II study of alemtuzumab (Campath®) in MDS patients who are likely to respond to immunosuppression.

Primary endpoints will be changes in peripheral blood counts (platelets, absolute neutrophil count, reticulocyte count, hemoglobin). Secondary endpoints (in transfusion-dependent patients) include improvement in the transfusion requirements (measured as decrease in the number of transfusion administered on "as needed basis"), duration of response, late effects of treatment, relapse and survival.

TABLE OF CONTENTS

- 1.0 OBJECTIVES
- 2.0 BACKGROUND
- 3.0 STUDY DESIGN
- 4.0 ELIGIBILITY ASSESSMENT
- 5.0 TREATMENT PLAN
- 6.0 CLINICAL EVALUATION
- 7.0 LABORATORY RESEARCH STUDIES
- 8.0 BIOSTATISTICAL CONSIDERATIONS
- 9.0 DATA AND SAFETY MONITORING
- 10.0 HUMAN SUBJECTS PROTECTION
- 11.0 PHARMACEUTICALS

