6.3 Post Treatment Monitoring Discharge Home Through 3 Months

After completing treatment, subjects will be followed by their home physician or at the Clinical Center and have blood work done as detailed below. Progress notes and laboratory results from home physicians will be faxed to the Research nurse, [name], [contact]. Subjects must be evaluated at the Clinical Center at the 1 month (+/- 7 days) and 3 month (\pm 7 days) time points

- Physical examination
- Complete blood counts with differential (weekly +/- 3 days)
- DAT (direct antiglobulin test) (months 1 and 3 +/- 2 weeks)
- Type and screen (at 1 month and 3 months only +/- 2 weeks or if clinically indicated)
- Acute care, mineral, hepatic and other panel (Home MDs: electrolytes, transaminases, urea nitrogen (BUN), serum creatinine, total bilirubin) (weekly +/- 3 days)
- EBV and CMV PCR in the blood (weekly +/- 3 days) for the first month, then every other week +/- 3 days) in the second month, and then monthly (+/- 2 weeks) starting in month 3
- Reticulocyte count (at 1 and 3 months only, Home MDs only if available)
- ECHO (at 3 months only +/- 2 weeks)
- Serum troponin-I (at 3 months only +/- 2 weeks)
- Thyroid function tests (at 3 months only +/- 2 weeks)
- Flow cytometry of the peripheral blood for GPI-cells (at 3 months only +/- 2 weeks)

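### Section 8.1's reticulocyte route to response states no pretreatment value, so read literally an unchanged, still-transfused subject could count in the 3-month test; probably a wording omission

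*Combined protocol and SAP*

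**What the plan says.** **The reticulocyte route.** Under Hemoglobin Response, Section 8.1 gives red-cell transfusion-dependent subjects a major response for "transfusion independence or an absolute reticulocyte count to" 60,000/µL or more. The two alternatives are joined by *or*, so transfusions need not stop. No pretreatment count and no size of rise are given.

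**The other count-based routes in 8.1.** Each states both a pretreatment limit and a rise: hemoglobin below 11 g/dL with a gain, platelets below 100,000/mm³ with a gain, ANC below 1500/mm³ with a gain.

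**Entry.** Section 4.1.2 lists alternatives joined by OR. One is "Anemia requiring transfusion support with at least one unit of packed red blood cells per month for greater than or equal to 2 months". Another is anemia shown by "hemoglobin <9 or a reticulocyte count <60,000". A subject who meets the first need not meet the second.

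**Appendix B.** Section 8.1 refers to it for detail. Its erythroid criterion (IIIa) for a major response reads "for RBC transfusion-dependent patients transfusion independence" and offers no reticulocyte alternative.

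**Confirmation.** Section 8.1 requires response to be "sustained on at least two serial measurements at least one week apart at landmark time points (3, 6 and 12 months"). Section 6.3 schedules "Reticulocyte count (at 1 and 3 months only, Home MDs only if available"), and Section 6.4 schedules the next count at month 6.

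**Use.** Section 8.3 tests complete plus partial response at 3 months against 30%.

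**The concern.** A response criterion should separate subjects who improved from those who did not. This route, taken word for word, is met by a level alone. A subject could enter on transfusion need with reticulocytes already at 60,000/µL or more, stay there, continue to be transfused, and be classed as a major hemoglobin responder. Two measurements a week apart would confirm the level, not a change.

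The classification feeds the trial's only formal efficacy decision. Two analysts working from Section 8.1 could class the same subject differently. Under the literal reading, a positive decision could rest partly on subjects in whom nothing happened.

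The two erythroid definitions also differ: a still-transfused subject credited on reticulocytes under 8.1 would not be a major erythroid responder under Appendix B IIIa.

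**Working it through.** **Step 1. Can an unchanged subject meet the text?**

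| Element | Place | Closes the gap? |
|---|---|---|
| Pretreatment reticulocytes below 60,000 required for the route | 8.1 | Not stated |
| Pretreatment reticulocytes below 60,000 required at entry | 4.1.2 | No; only one of several alternatives |
| Detailed criteria | Appendix B IIIa | No; route absent |
| Two measurements a week apart | 8.1 | No; confirms a level |
| Transfusions must stop | 8.1 | No; joined by *or* |

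One further link is needed. The route is listed as a major response, while partial response is defined as one or more minor responses. The subject enters the 3-month count only if a major response also qualifies as partial. That is the natural reading, because otherwise major responders short of complete response would be left out of the primary count, but it is not written down.

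**Step 2. Reproduce the design.** Inputs from 8.3: 19 subjects in stage 1, continue with 7 or more responders; 39 in total, success with 17 or more. With X ~ Bin(19, p) and Y ~ Bin(20, p),

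P(success) = Σ over x = 7 to 19 of P(X = x) · P(Y ≥ 17 − x).

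At p = 0.30 this is 0.0455, with early-stopping probability 0.666. At p = 0.50 it is 0.8036. The stated 0.05 and 0.80 are met.

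**Step 3. Illustration.** Suppose k of the 39 subjects are always counted, are spread at random over the two stages, and the other 39 − k respond with probability 0.30. The documents give no value for k. Let j be the number of the k who fall in stage 1. Then X ~ Bin(19 − j, 0.30), Y ~ Bin(20 − k + j, 0.30), the trial continues if X + j ≥ 7, and it succeeds if X + Y + k ≥ 17:

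P(success) = Σ over j of [C(k, j) · C(39 − k, 19 − j) / C(39, 19)] · Σ over x ≥ 7 − j of P(X = x) · P(Y ≥ 17 − k − x).

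For k = 1: the subject is in stage 1 with probability 19/39 = 0.487 (success 0.0717) or in stage 2 with probability 20/39 = 0.513 (success 0.0674). The result is 0.487 × 0.0717 + 0.513 × 0.0674 = 0.0695.

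| k (assumed) | Chance of declaring success |
|---|---|
| 0 | 0.0455 |
| 1 | 0.0695 |
| 2 | 0.1034 |
| 3 | 0.1494 |
| 4 | 0.2093 |

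If a rise from below 60,000 is required, k = 0. If p in 8.3 means response exactly as 8.1 words it, these subjects are part of p, and the error at p = 0.30 stays at 0.0455.

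**Step 4. Confirmation.** Blood counts are weekly to month 3 (6.3), but reticulocytes are scheduled only at months 1 and 3, then month 6. If both measurements must belong to the 3-month landmark, no second reticulocyte count is scheduled there. If the wording allows the second value at a later landmark, month 6 could supply it. The text does not say which.

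**The case against.** The best reply is that the protocol plainly meant a rise. The word *to* before the threshold reads as though a verb of increase dropped out. The synopsis says "Primary endpoints will be changes in peripheral blood counts (platelets, absolute neutrophil count, reticulocyte count, hemoglobin"). Complete response in 8.1 is normalization of the lines that were affected, which limits reticulocytes to subjects abnormal beforehand. The threshold matches the abnormality named in 4.1.2. No passage supports crediting an unchanged count. This stands, and it is why the gap is best called an omission.

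A second reply is that the literal reading is selective: it takes *to 60,000* strictly but reads the partial-response definition generously. This also stands; the concern depends on that unstated step.

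A third is that the transfusion-dependent branches in 8.1 give no numeric pretreatment count anywhere. That is true, but the others require a change of status (independence, or halved transfusions). The reticulocyte branch alone requires neither.

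A fourth is that follow-up has ended (10.4), so any rewording now comes after the fact. This limits the remedy to a disclosed clarification with sensitivity analysis. The study is still in data analysis, so the classification rule still matters.

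**Conclusion.** The gap is real and minor. Section 8.1 omits a pretreatment condition that its other count-based routes have, and neither 4.1.2 nor Appendix B supplies it. The consequence rests on three things: a literal reading of the route, a major response counting as partial, and at least one transfusion-dependent subject with reticulocytes already at 60,000/µL or more who qualifies on nothing else. The documents do not say whether any such subject exists.

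A reader might infer three stronger points that the documents do not support.

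- *The test's type I error is inflated.* The 7.0% to 20.9% figures (k = 1 to 4) need an assumed k and a definition of true response that differs from the protocol's. On response as written, the error is 4.5% and the question is only what the endpoint measures.
- *The thin reticulocyte schedule makes the gap worse.* If a second 3-month value is required and missing, a reticulocyte-only subject cannot be confirmed. That limits false credit, though it leaves the subject's status unclear.
- *The historical comparison is invalid.* Section 8.2 plans a comparison with earlier NIH studies but does not name the transfusion-independence figures in 2.4.1 (21 of 61; 3 of 18) as the comparator.

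**What to change.** 1. State in 8.1 that the reticulocyte route applies only to red-cell transfusion-dependent subjects with pretreatment reticulocytes below 60,000/µL who rise to 60,000/µL or more, and reconcile it with Appendix B IIIa.
2. Report the 3-month response rate and the two-stage decision with and without subjects who qualify on reticulocytes alone, and state how many of those lack a confirming value.
3. If the 2.4.1 figures are used as the historical comparator, set them against the transfusion-independence proportion from 8.2.1.
4. Disclose all of this as a clarification and sensitivity analysis made after follow-up ended.

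The cost is one sentence and a few table rows. Pretreatment and 3-month reticulocyte counts are already scheduled (6.1, 6.3), so no new data are needed. The response rate may come out slightly lower. Dropping the reticulocyte route would align the erythroid criterion with IIIa but would not make the overall rate fully comparable with Appendix B, which also says "Improvements must last at least 2 months in the absence of ongoing cytotoxic therapy".
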